## 1.2. List Of Abbreviations

AST	Aspartate aminotransferase
BCC	Basal Cell Carcinoma
BMI	Body mass index
CK	Creatinine Kinase
COVID-19	Novel Coronavirus (Sars-Cov-2)
CPI	Coordinating Principal Investigator
CRF	Case Report Form
CT	Computed Tomography
DSMC	Data and Safety Monitoring Committee
eCRF	Electronic Case Report Form
EDC	Electronic Data Capture
FAS	Full Analysis Set
FBC	Full Blood Count
MSU	Mid-Stream Urine
MTD	Maximum Tolerated Dose
NHMRC	National Health and Medical Research Council
OTC	Over The Counter
PGIC	Patients General Impression of Change
PICF	Patient Information and Consent Form
PD	Pharmacodynamic
PK	Pharmacokinetics
PP	Per Population
QST	Quantitative Sensory Test
ULN	Upper Limit of normal

## 2. PROTOCOL SYNOPSIS

Title	A Two-part Proof-of-Concept Study Assessing the Safety and Efficacy of LAT8881 in Lumbar Radicular Pain.
Short Title	LAT-NP-002
Sponsor	Lateral Pharma Pty Ltd
Protocol Number	LAT-NP-002
Study Phase	1b
Primary Objective	
Part A: Evaluate the safety and tolerability of intravenous LAT8881 using an ascending dose schedule
 
Part B: Evaluate the analgesic efficacy of LAT8881 in patients with lumbar radicular pain

Secondary Objective(s)	
Part A: Evaluate the plasma concentrations and the PK properties of LAT8881 administered as an IV injection in healthy participants using a dose escalating design Establish the dose regimen for Part B of the study
 
Part B: Evaluate the effect of Intravenous LAT8881, compared with placebo, on VAS pain scores at rest Confirm the safety of IV LAT8881 in participants with lumbar radicular pain

Exploratory Objectives	
Part A: Collect blood samples to investigate a pharmacodynamic assay and/or biomarkers of LAT8881 activity
 
Part B: Evaluate mechanical Quantitative Sensory Test (QST) assessment on affected lower limb using Von Frey Aesthesiometer on two occasions, once prior to dosing and once post dosing. Evaluate the effect of Intravenous LAT8881, compared with placebo, on VAS pain scores during straight-leg raise nerve stretch Collect blood samples to investigate (and possibly validate) a pharmacodynamic assay and/or biomarkers of LAT8881 activity

Primary Endpoints	
Part A
 
Safety and Tolerability
 
 
• Incidence, severity, and causality of AEs
 
• Incidence and severity of clinical laboratory abnormalities
 
• Change from baseline in vital signs (BP, temperature, respiratory rate, and heart rate)
 
• Change from baseline in 12-lead ECG parameters
 

	
Part B: the change in pain from baseline during and after each infusion on a VAS 0-10 numerical rating scale of “pain now” with measures taken as the infusion starts and at 15 minute intervals for the first hour, then every thirty minutes for an additional two hours, then hourly until 6 hours from infusion commencement

Secondary endpoints	
Part A:
 
 
• Pharmacokinetic profile
 
 
Part B:
 
 
• Comparison of radicular “pain now” scores as peak change from baseline and area under the curve comparing the two arms over the full six hours
 
• Comparison of Patients general impression of change between dosing arms
 
• Adverse event rates in each dosing arm
 

Exploratory endpoints	
Part A:
 
 
• Pharmacodynamic assay and/or biomarkers of LAT8881 activity.
 
 
Part B:
 
 
• Mechanical QST assessment using Von Frey Aesthesiometer
 
• Evaluate the effect of Intravenous LAT8881, compared with placebo, on VAS radicular pain scores during straight-leg raise nerve stretch
 
• Bang Binding Index assessment, whereby participant will be asked to record which dosing occasion they believe they got the active IP.
 
• Pharmacodynamic assay and/or biomarkers of LAT8881 activity.
 

Study Design	
Part A:
 
This is a double-blind, randomized, placebo-controlled, single ascending dose study within 8 healthy volunteers of intravenous administration of LAT8881 over 5 minutes.
 
Part A of the Study will enrol 8 participants, each participant has three treatment days, 1 infusion per dosing day on days 1, 4 and 7 as well as two short visits for safety blood sampling on Day 3 and 6. The 8 subjects will be split into two groups of 4 subjects each (3 IMP and 1 placebo), with the two groups dosed a few days apart.
 
Participants arrive on the morning of treatment day, receive a single infusion, leave that afternoon (no overnight stay). Participants will be dosed at staggered intervals as determined by PI. .
 
Treatments are on Days 1 (0.8 mg/kg), Day 4 (1.2 mg/kg) and Day 7 (1.8 mg/kg) or placebo to allow sufficient washout and consideration of any safety observed following each dosing day. Day 3 and 6 safety blood results must be review prior dosing on the following day.
 
Participants will fast for 8 hours pre-dose and 4 hours post dose for each dosing occasion.

	
Participants are randomised, so on each treatment day per group, 3 participants receive LAT8881 and 1 receive placebo (different participants to receive placebo each treatment day)
 
Participants will remain at the clinic until 6 hours post-infusion in order to collect blood samples for PK analysis and for review of safety and tolerability. Safety assessments will be reviewed in a clinic exit visit 7 days after the last infusion.
 
Part B:
 
This is a placebo-controlled randomized double blind cross-over safety and efficacy study of LAT8881.
 
Participants will be randomized into two groups and will receive either a single 1.8 mg/kg dose of LAT8881 or placebo via intravenous administration over 10 minutes on two consecutive days.
 
Participants will be randomly assigned to one of two groups, active then placebo or placebo then active.
 
After passing screening, participants will be admitted for two nights:
 

1. A study staff member will contact the participant for 3 consecutive days the week prior to obtain a verbal pain score out of 10 to confirm that their mean resting radicular pain meets the study inclusion criteria (pain score on each of the 3 days must be <math>\geq 3</math>)

2. The participant will arrive the evening prior to dosing, and will complete a final review of inclusion/exclusion criteria.

3. Baseline assessments will be completed on the first day of dosing prior to IMP administration

4. The participant will then receive their first dose.

5. Collection of blood samples for PK/ PD analysis and assessments for review of safety, tolerability and efficacy are listed in the Schedule of Assessments.

 
The participants will stay overnight.
 
If the PK from the Part A demonstrates elimination in < 6 hours (assessed by concentration below LOQ of assay),
 

6. the following morning the participants will cross-over and receive their second dose.

7. Collection of blood samples for PK analysis and assessments for review of safety, tolerability and efficacy are listed in the Schedule of Assessments.

8. Participants will remain at the clinic until 6 hours post the second infusion and then may be discharged.

 
At the discretion of the Investigator and in consultation with the Study Sponsor, the requirement for subjects to be admitted to the clinic from the evening before Day 1 through to discharge at the end of Day 2 can be waived. In such circumstances, items 1 through 8 above will still apply, with the following modification to item #2:

--	---

	
 
- During the morning of Day 1 the following will be undertaken prior to dosing: a) a complete final review of inclusion/exclusion criteria, b) a written account of the activities the participant undertook on Day 0.
 
- Prior to dosing on Day 2, a written account of the activities the participant undertook after discharge at the end of Day 1.
 
 
Safety assessments will be reviewed 7 days after the last infusion by clinic exit visit.
 
Participants will fast for 8 hours pre-dose and 4 hours post dose for each dosing occasion.

Sample Size (by treatment group)	Part A: 8 healthy participants Part B: Up to 20 participants with a history of lumbar radicular pain
Inclusion Criteria	Participants who meet all the following inclusion criteria may be included in the study: 
 
1. Male or female healthy participants, aged 18-49 years inclusive at screening;
 
2. Body mass index (BMI) of <math>\geq 19.0 \text{ kg/m}^2</math> to <math>\leq 32.0 \text{ kg/m}^2</math> at screening;
 
3. The participant must voluntarily provide written informed consent prior to any study procedures being performed and is willing and able to comply with procedures required in this protocol.
 
4. A female participant is eligible to participate if she is not pregnant, not breastfeeding, and at least 1 of the following conditions applies: 
 
a. Not of childbearing potential, defined as surgically sterile (documented hysterectomy, bilateral salpingectomy or bilateral oophorectomy) or postmenopausal (no menses for 12 months without an alternative medical cause. A high follicle stimulating hormone (FSH) level in the postmenopausal range may be used to confirm a postmenopausal state in women not using hormonal contraception or hormonal replacement therapy; however, in the absence of 12 months of amenorrhea, a single FSH measurement is insufficient);
 
b. Of childbearing potential and agrees to use a highly effective method of contraception consistently during the treatment period and for at least 60 days following completion of study.
 
c. A male participant with a female partner of childbearing potential is eligible to participate if he agrees to use highly effective contraception during the treatment period and for at least 60 days after the last dose of study treatment and refrains from donating sperm during this period;
 
 
 
5. Females of childbearing potential must have a negative pregnancy test at screening (serum) and Day 1 (urine).
 
6. Willing to be tested for SARS-CoV-2 infection if requested
 
7. Agree to adhere to the current state and national advice regarding minimizing exposure to severe acute respiratory syndrome coronavirus 2 (SARS-CoV-2) from the first Screening visit until the
 

	
EOS/ETV. A SARS-CoV-2 Test will be taken if clinically indicated and in line with local processes.
 
For Part B of the study, the following criteria is in addition to criteria 3-7:
 
 
8. Male or female participants with sciatic pain, aged 18 years and above
 
9. Body mass index (BMI) of <math>\geq 19.0 \text{ kg/m}^2</math>
 
10. Presenting with a history of sciatic pain, radiating into a lower limb, of lancinating, burning, stabbing or electric quality, of duration of more than 3 months.
 
11. Pain scores (VAS) for average daily leg pain at rest at the relevant nerve root of a mean of <math>\geq 4/10</math> and <math>\leq 9/10</math> for 3 days during the week prior to treatment, with a minimum of <math>\geq 3/10</math> on any day.
 
12. Demonstration of disc herniation within 6 months by CT or MRI at a segmental level consistent with the clinical features.
 
13. The site of disc herniation must affect L1-2, L2-3, L3-4, L4-5 or L5-S1.
 
14. The patient is willing to keep all analgesic medication and other therapy usage [such as physiotherapy, acupuncture, or transcutaneous electrical nerve stimulation (TENS)] stable or decreased in the week prior to, and a week after, IP administration.
 
15. The patient is in good general health, with the exception of the presenting condition under study, as determined by medical and psychiatric history, physical examination, ECG, serum chemistry and hematology, urinalysis and serology.
 

Exclusion Criteria	
Any of the following will exclude potential participants from both parts of the study:
 
 
1. History or evidence of a clinically significant disorder (including psychiatric), condition, or disease that, in the opinion of the investigator and medical monitor or designee, would pose a risk to participants safety or interfere with the study evaluation, procedures, or completion;
 
2. History or presence of conditions known to interfere with the distribution, metabolism, or excretion of drugs;
 
3. Unwillingness to abstain from alcohol from 24 hours prior to investigational product administration, during confinement in the study site until discharge from the confinement period.
 
4. A positive urine drug screen or alcohol breath test at screening; unless prescribed medication therapy for participants enrolled in Part B
 
5. History of surgery or major trauma within 12 weeks of screening, or surgery planned during the study;
 
6. Has any local skin infection that could compromise the injection site or have insufficient venous access.
 
7. History of significant neurological diseases, including stroke, TIAs, seizures, and vascular malformations.
 
8. Positive screen for human immunodeficiency virus (HIV), hepatitis B virus surface antigen (HBsAg) or hepatitis C virus antibody (HCV);
 

	
9. Treatment with any investigational product within 30 days or 5 half-lives (whichever is longer) prior to baseline visit, or concurrent participation in a clinical study with an investigational product or device;
 
10. Use of prescription or over the counter medications within 14 days of investigational product administration and during the study, with the exception of current medications provided the dose has been stable for at least 14 days, contraceptive medications, paracetamol, oral non-steroidal anti-inflammatory agents and vitamins or other medications that, in the opinion of the investigator, will not pose a risk to participants safety or interfere with the study evaluation, procedures or completion;
 
11. History of cancer, with the exception of successfully treated non-metastatic basal cell and squamous cell carcinoma;
 
12. Treatment involving chemotherapy or the known possibility of chemotherapy in the future
 
13. Participant has a known history of active or latent TB, except documented and complete adequate treatment of TB;
 
14. Has clinically significant laboratory abnormality as determined by the investigator deemed clinically significant by the investigator; inclusive of Alanine aminotransferase (ALT) and aspartate aminotransferase (AST) <math>\geq 1.5 \times</math> the upper limit of normal (ULN)
 
15. Has a history of substance abuse in the past 5 years or as determined by PI.
 
16. Is unwilling to refrain from donating blood products or plasma within 30 days prior to or post the study drug administration.
 
17. Patient has a documented history of allergy or intolerance to components of the study drug.

For Part B of the study, the following criteria is in addition to criteria 1-18:	
	
18. Has a history of significant pain unrelated to disc herniation that, in the opinion of the investigator, would significantly compromise assessment of leg radicular pain.
 
19. Has radiological evidence of foraminal stenosis or of clinically significant spinal stenosis .
 
20. Has had lumbar back surgery related to the specific disc(s).
 
21. Has received an epidural corticosteroid injection within 3 months of screening.
 
22. Has an ongoing worker's compensation claim, disability claims, or litigation related to any pain problem.
 
23. Has a history of chronic infection, including TB, Hep.B, Hep.C, or HIV.
 
24. Has a history of demyelinating disease such as Multiple Sclerosis, Neuromyelitis Optica, or Optic Neuritis.
 
25. Has significant spinal stenosis or spondylolisthesis (Grade 2 or higher).
 
26. Has a history of diabetic neuropathy or peripheral neuropathy in the lower extremities.

Investigational Product	
LAT8881 is administered via an infusion pump at a constant rate. The LAT8881 formulation will be presented in a pre-filled syringe containing the following:
 
 
- LAT8881 10 mg/ml (active)
 
- DSPE-PEG2000 20 mg/ml (Buffer)
 
- Mannitol 47 mg/ml (Tonicity)
 
- Sodium Hydroxide 0.33 mg/ml (Buffer)
 
 
The placebo formulation will be presented as above but without the LAT8881 active.

Dosage Regimen	
Part A: LAT8881 (or placebo) is administered at a dose of 0.8 mg/kg, 1.2 mg/kg and 1.8 mg/kg via an infusion pump at a constant rate over 5 minutes.
 
Part B: LAT8881 (or placebo) is administered at a dose of 1.8 mg/kg via an infusion pump at a constant rate over 10 minutes.

Duration of Treatment	
Part A: Three single doses of LAT8881 or placebo (Day 1, Day 4 and Day 7)
 
Part B: Two single doses, one of LAT8881 and one of placebo over two dosing occasions.

Statistical Methods	
A maximum of 8 participants in Part 1 and 20 participants in Part 2 will be randomised to the trial, to achieve a sample size of up to 28 participants completing all study interventions. There will be an interim analysis after at least 10 participants in Part B complete the Study Per Protocol.

## 3. SCHEDULE 1 OF OBSERVATIONS AND PROCEDURES PART A

Procedure	Day -30 to -2	Day 1/Day 4/Day 7 (hours)												Day 3/ 6	Day 14/ ETV
	Screening	Pre- Dose	Dose	5 min	0.25	0.5	1	1.5	2	2.5	3	4	6 Discharge	Day prior dosing 	+/- 2 day
Informed consent	x														
Medical history	x	x													
Inclusion/exclusion criteria	x														
Demography	x														
Physical examination, height, weight	x														
Symptom-directed physical exam		x											x		x
Pregnancy test (WOCBP) 	x	x													x
Urine drug screen, Urinalysis and Alcohol breath test 	x	x													
SARS-CoV-2 Test 															
HIV, Hepatitis B & C screening	x														
Clinical laboratory tests	x												x	x	
12-lead ECG	x	x							x				x		x
Vital signs	x	x			x	x	x	x	x	x	x	x	x		x
Spot pulse oximetry	x	x			x	x	x	x	x	x	x	x	x		x
Randomization		x													
Dose administration 			x												
AE review				x	x	x	x	x	x	x	x	x	x		x
Concomitant medication review	x	x	x	x	x	x	x	x	x	x	x	x	x		x
PK 		x		x	x	x	x	x	x			x	x		
PD 		x		x	x	x	x	x	x			x	x		
Discharge													x		

\*# Participants who withdraw early from the study will be encouraged to return to the clinic for an ETV assessment.

\* Participants may require an unscheduled visit to address safety issues and/or for any additional PK and/or PD sample collection as required.

1 All WOCBP will have a serum pregnancy test at Screening and at the ETV visit, if applicable. Urine pregnancy tests will be performed for WOCBP at all other specified subsequent visits. If a urine pregnancy test is positive, it must be confirmed by a serum pregnancy test.

2. Urine Drug Screen and Alcohol Breath Test will be performed in clinic. A urine dipstick will be completed at all visit. In the event of positive Leukocytes and/or nitrates that urine sample will be sent to the local labortaotry for a microscopic examination.

3. SARS-CoV-2 Test will be taken if clinically indicated and in line with local processes.  
 4. All participants will fast 8 hours prior and 4 hours after the study drug administration  
 5. Samples must be taken with enough time that results are available prior to planned IP dosing on the following morning.  
 6. Pre-dose, 5 ± 1 min, 15 ± 2 min, 30 ± 2 min, 60 ± 5 min, 2 h ± 10 min, 4h ± 20 min, 6h ± 30 min post-dose.

#### 4. SCHEDULE 1 OF OBSERVATIONS AND PROCEDURES PART B

Procedure	Day -30 to -2	Day 1/Day 2 (hours)															Day 9/ ETV		
	Screening	Pre Dose	Dose	5min	10 min	15 min	20 min	30 min	45 min	1	1.5	2	2.5	3	3.5	4	5	6	+/ - 1 day
Informed consent	x																		
Medical history	x																		
Inclusion/exclusion criteria	x	x																	
Demography	x																		
Physical examination, height, weight	x																		
Symptom-directed physical exam		x															x	x	
MRI or CT if >6mths 	x																		
Sciatic Pain History	x																		
3 Day NRS Pain Scores 		x																	
Pregnancy test (WOCBP) 	x	x																x	
Urine drug screen, Urinalysis and Alcohol breath test 	x	x																	
SARS-CoV-2 Test 																			
HIV, Hepatitis B & C screening	x																		
Clinical laboratory tests	x	x															x	x	
12-lead ECG	x	x										x			x		x	x	
Vital signs	x	x								x	x	x	x	x	x	x	x	x	
Spot pulse oximetry	x	x								x	x	x	x	x	x	x	x	x	
Pain scores (VAS)		x			x			x	x	x	x	x	x	x	x	x	x	x	

Provocation Assessment with VAS		x				x		x	x	x	x	x	x	x	x	x	x	x	x	x	
Patient General Impression of Change 																			x		
QST (von Frey) 		x										x				x					
Randomization		x																			
Dose administration 			x																		
AE review				x		x		x	x	x	x	x	x	x	x	x	x	x	x	x	
PK Sampling 		X		x	x		x	x	x	x									x		
PD Sampling 		x		x	x		x	x	x	x								x			
Concomitant medication review												x							x		
Bang Binding Index assessment 																		x			
Discharge 																		x			

\*# Participants who withdraw early from the study will be encouraged to return to the clinic for an ETV assessment.

\* Participants may require an unscheduled visit to address safety issues and/or for any additional PK and/or PD sample collection as required.

1 All WOCBP will have a serum pregnancy test at Screening and at the ETV visit, if applicable. Urine pregnancy tests will be performed for WOCBP at all other specified subsequent visits. If a urine pregnancy test is positive, it must be confirmed by a serum pregnancy test.

2. Urine Drug Screen and Alcohol Breath Test will be performed in clinic. A urine dipstick will be completed at all visit. In the event of positive Leukocytes and/or nitrates that urine sample will be sent to the local labortaotry for a microscopic examination.

3. SARS-CoV-2 Test will be taken if clinically indicated and in line with local processes.

4. All participants will fast 8 hours prior and 4 hours after the study drug administration

5. Staff to contact the participant for 3 consecutive days during the week prior to dosing for documentation of daily pain scores

6. Not required if participant has current imaging available within the last 6 months

7. Mechanical Quantitative Sensory Test (QST) assessment using Von Frey Aesthesiometer will be completed by trained staff members

8. Pre-dose, 5 (mid infusion), 10 (end of infusion)  $\pm$  1 min, 20  $\pm$  1 min, 30  $\pm$  2 min, 45 min  $\pm$  5 min, 60 min  $\pm$  5 min, 6h  $\pm$  30 min from the start of the infusion of the dose.

9. Completed 6 hours post dose on Day 2 only

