#### Part B:

- Evaluate the effect of Intravenous LAT8881, compared with placebo, VAS pain scores at rest
- Confirm the safety of LAT8881 in participants with lumbar radicular pain

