### Part B:

LAT8881 is administered at a dose of 1.8 mg/kg via an infusion pump at a constant rate over 10 minutes.

The placebo formulation will be presented as above but without the LAT8881 active.

To minimise potential local infusion site irritation or reaction, the LAT8881 infusion will be administered in line with a continuous infusion of 5% Dextrose Solution (50 g of glucose in water for injection, or equivalent). The dextrose solution infusion will commence approximately 30 minutes pre-dose and continue until the participant ceases fasting.

The rate of dextrose solution will be 80mls/hr. The IV dosing/ Normal Saline infusion cannula will be inserted into the opposite arm to the PK sampling IV Cannula to avoid any dilution of the PK samples.

Further details on the administration process can be found in the Pharmacy Manual.

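### Part B schedules no vital signs or oximetry from pre-dose until 1 h after infusion start, unlike Part A, so its vital-sign tables cannot describe the infusion or the first hour

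*Protocol*

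**What the plan says.** Protocol section 4 sets the Part B time axis as "Screening Pre Dose Dose 5min 10 min 15 min 20 min 30 min 45 min 1 1.5" and onward to 6 h and Day 9. The two rows at issue begin "Vital signs x x x x x" and "Spot pulse oximetry x x x x x". Quoted this way the rows lose their blank cells, and the blanks are the point. By cell position, marks one and two (in the oximetry row, "Spot pulse oximetry x x") are screening and pre-dose, and the third is in the 1 h column.

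The Part A row in protocol section 3, "Spot pulse oximetry x x x x x x", looks the same when collapsed. By position, however, its third and fourth marks are at 0.25 and 0.5 h.

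On dosing, the Part B text of protocol section 11 says "LAT8881 is administered at a dose of 1.8 mg/kg via an infusion pump at a constant rate over 10 minutes". Footnote 8 of the Part B schedule puts PK and PD samples inside the same window: "Pre-dose, 5 (mid infusion), 10 (end of infusion", then 20, 30, 45 and 60 min, all counted from infusion start.

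Protocol 6.3 gives Part B the secondary objective "Confirm the safety of LAT8881 in participants with lumbar radicular pain". Protocol 21.3.4 and SAP 12.4.2 plan vital-sign summaries for Part B as well as Part A.

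**The concern.** Part B is where patients first receive 1.8 mg/kg intravenously. At a constant rate, the plasma level would be expected to peak around the end of the infusion. If the first scheduled blood pressure, heart rate, respiratory rate and saturation after dosing come at 1 h, a short-lived change without symptoms has no scheduled reading in which to show.

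The Part B change-from-baseline tables could then look clean because nothing was measured early, and a reader could take that as evidence of haemodynamic safety during dosing. There is also a knock-on effect. Protocol section 16 names vital signs as one way adverse events are found, and 20.7.1 turns clinically significant abnormal findings into adverse events. A change that nobody measured would be absent from those data too.

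**Working it through.** The plan states no figure on this point, so the check is a cell-by-cell reading of the two schedules.

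**1. Marks by column**

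| Row | Marks up to 1 h | Later marks |
|---|---|---|
| Part B vital signs and oximetry | screening, pre-dose, 1 h | 1.5, 2, 2.5, 3, 3.5, 4, 5, 6 h |
| Part A vital signs and oximetry | screening, pre-dose, 0.25, 0.5, 1 h | 1.5, 2, 2.5, 3, 4, 6 h, Day 14 |
| Part B adverse-event review | 5, 15, 30, 45 min, 1 h | continues |
| Part B PK sampling | pre-dose, 5, 10, 20, 30, 45 min, 1 h | one late sample |

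Part B has six post-start columns before 1 h (5, 10, 15, 20, 30 and 45 min). None is marked for vital signs or oximetry. Part A has two readings in its first half hour.

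**2. Length of the gap.** The first reading is 60 min after infusion start, so 60 − 10 = 50 min after the infusion ends. This assumes the row uses the same clock as footnote 8 and the primary endpoint, both counted from infusion start. If it counted from infusion end, the gap would be longer.

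**3. Could it be an extraction fault?** Parts of this table are misaligned. The first post-dose pain score falls under 10 min although the endpoint says 15 min, the general-impression mark falls under Day 9, and vital signs have no Day 9 mark. Three checks follow.

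- The endpoint text puts pain scores at 15, 30, 45 and 60 min. The pain row has three post-dose marks before the column where vital signs begin, so vital signs begin at its fourth, which is 60 min.
- The early PK marks match footnote 8, and the sensory-test marks at 2 and 4 h match protocol 9.6.17.
- Moving the vital-signs row one column left makes the first reading 45 min; one column right makes it 1.5 h. Either way 5 to 30 min stays empty.

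**4. Does other text fill the gap?** Protocol 9.6.6 refers back to the schedules. SAP 12.4.2 summarises what is scheduled. SAP 3.2.6 lists 5 to 45 min, but as one common list for all visit-based tables. The first post-dose ECG mark is in the 2 h column. Unscheduled readings are not barred, but SAP section 3 keeps unscheduled visits out of visit-based summary tables, so such readings would probably reach only the listings.

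**5. How far does Part A stand in?** Per protocol 7.3, 6 of 8 participants are on active drug at each dose level. They are healthy, aged 18–49, with BMI up to 32. Part B has no upper age or BMI limit. The nominal rate at 1.8 mg/kg is 1.8/5 = 0.36 mg/kg/min in Part A and 1.8/10 = 0.18 mg/kg/min in Part B. Part A has no vital-sign mark in its 5 min column, the nominal end of its infusion.

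**6. Illustration only.** The documents give no half-life. Assume mono-exponential decline with half-life h minutes. The share of the end-of-infusion level left is 2^(−50/h) at Part B's 1 h reading. At Part A's 15 min reading it is 2^(−10/h) if timed from infusion start, or 2^(−15/h) if timed from infusion end; the Part A text does not settle which.

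| Assumed h (min) | Part B, 1 h | Part A, 15 min from start | Part A, 15 min from end |
|---|---|---|---|
| 10 | 3% | 50% | 35% |
| 20 | 18% | 71% | 59% |
| 30 | 31% | 79% | 71% |
| 60 | 56% | 89% | 84% |

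**The case against.** The best defence is that Part A came first. It scheduled readings at 15 and 30 min after the same 1.8 mg/kg, at twice the nominal rate, and safety and PK data went to review before Part B. Change in vital signs is a listed endpoint only in Part A; Part B's safety endpoint is adverse-event rates. Part B dosing is supervised, adverse events are reviewed at 5, 15, 30 and 45 min, and halting rules apply. Two parts with different aims may have different schedules, so the difference is not in itself a contradiction.

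Most of that stands, and it limits the point without removing it. Adverse-event review picks up symptoms; it does not schedule a blood pressure or saturation reading. Part A covers few people, all healthy and under 50.

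A reader might infer more than the documents support:

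- *That acute reactions in patients go unrecorded.* Symptomatic ones are covered, and unscheduled readings are allowed. Only scheduled objective readings are missing.
- *That the drug has largely gone by 1 h.* The range above is 3% to 56%, driven wholly by assumed half-lives.
- *That the plan expects concentrations below quantification before 6 h.* The protocol synopsis and SAP 2.1.2 make this a condition for next-day crossover, to be shown by Part A.
- *That stable medication sets Part B patients apart.* Exclusion 10 allows it in both parts, and inclusion 15 requires Part B patients to be otherwise in good general health. The differences that hold are age, BMI and the presenting condition.
- *That matching Part A would capture the peak.* Part A has no end-of-infusion reading either.

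**Conclusion.** The gap holds, in bounded form. As extracted, Part B schedules no vital signs or oximetry between pre-dose and 1 h after infusion start. This leaves the infusion and about 50 minutes after it without a scheduled objective reading, where Part A has two in the first half hour. No reason is given.

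The consequence is a limit on what can be concluded: the Part B vital-sign tables cannot show an asymptomatic transient change in that window, and so cannot support a haemodynamic safety statement about it. It is worth correcting because it bears on patient safety and a stated objective, and the correction is cheap.

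The conclusion rests on the column reading, which survives a one-column shift for 5 to 30 min, and on timing from infusion start. It does not rest on any half-life. The exact first timepoint needs confirming in the source table.

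**What to change.** First, check the Part B vital-signs and oximetry rows in the source table.

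If the gap is confirmed, reconcile those rows with Part A's first-hour coverage, or state why the parts differ. The monitoring times are for the sponsor to choose; none is proposed here. Staff already attend in the first hour for PK, pain scores and adverse-event review, so the cost is a schedule amendment and a few readings. The downside is more handling around the early pain scores: protocol 9.6.6 requires a 5-minute rest before vital signs, which has to fit around the leg-raise assessments. SAP 12.4.2 needs no change, since it follows whatever is scheduled.

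SAP 2.5 records 14 completers at the interim analysis and a recommendation to close the study on 12 May 2023, so an amendment may come too late. If the schedule stays or dosing is finished, add a statement to the SAP and the report that Part B scheduled vital signs and oximetry begin at 1 h and cannot support a haemodynamic safety conclusion for the infusion or first hour. Any unscheduled early readings can be listed and identified as such. This costs only text.
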